6.2.1. Study Completion and End of Trial

This study will be considered complete (that is, the scientific evaluation will be complete [study completion]) when the primary and secondary study objectives have been met. “End of trial” refers to the date of the last visit or last scheduled procedure for the last patient.

The end of trial occurs after study completion and after the last patient has discontinued study treatment and completed any applicable continued access follow-up.

6.2.2. Continued Access Period

Patients who are still on study treatment at the time of study completion may continue to receive study treatment if they are experiencing clinical benefit and no undue risks.

[figure not shown]
Continued access will apply to this study only if at least one patient is still on study treatment when study completion occurs. Lilly (the sponsor) will notify investigators when the continued access period begins.

The sponsor may allow patients to enroll in an LY3022855 “rollover” protocol to provide long-term continued access for patients enrolled in this study.

Patients must sign a new ICF before continued access is provided.

The patient's continued access to study treatment (Visits 501-5XX) will end when the patient and investigator agree that the patient will no longer continue to receive study treatment. Continued access follow-up (Visits 901 [30-day] and 902 [90-day, only for durvalumab and tremelimumab safety]) will begin the day after the patient and the investigator agree that the patient will no longer continue to receive study treatment. Continued access follow-up for Visit 901 lasts approximately 30 days (± 7 days); Visit 902 occurs 90 days (± 7 days) after the patient and investigator agree that the patient will no longer continue to receive study treatment. Follow-up procedures will be performed as shown in the Continued Access Schedule in [Attachment 1](#).

Figure JSCC.9 presents the sequence of study periods, including continued access.

^a Lilly will notify sites when the continued access period begins and ends.

^b Primary and secondary objectives have been met. Lilly will notify sites when study completion occurs.

^c End of trial occurs at the last visit or last scheduled procedure for the last patient.

Figure JSCC.9. Continued access diagram.

Patients who are in short-term follow-up (Visit 801 [30-day] or Visit 802 [90-day]) when the continued access period begins will continue in short-term follow-up until the 30-Day/90-Day Follow-Up visit is completed.

6.3. Discontinuations

The reason for and date of discontinuation will be collected for all patients. The date of discontinuation from study treatment is to be reported on the electronic case report form (eCRF). Patients who discontinue will have follow-up procedures performed as shown in the Study Schedule (Attachment 1).

If a patient withdraws informed consent, he or she must not be contacted unless he or she has explicitly provided permission and consent. Lilly may continue to use previously collected medical research data prior to the withdrawal consistent with the original authorization.

Refer to Section 7.6.1 for conditions under which patients may be replaced.

6.3.1. Discontinuation of Patients Inadvertently Enrolled

If the sponsor or the investigator site identifies a patient who did not meet enrollment criteria and who was inadvertently enrolled, a discussion must occur between the sponsor's clinical research physician (CRP)/clinical research scientist (CRS) and the investigator to determine if the patient may continue in the study. If both agree that it is medically appropriate to continue, the investigator must obtain documented approval from the sponsor's CRP/CRS to allow the inadvertently enrolled patient to continue in the study with or without study treatment.

6.3.2. Discontinuation of Patients from Study and/or Study Treatment

Patients who are discontinued from the study treatment will have follow-up procedures performed as shown in the Study Schedule ([Attachment 1](#)).

Patients will be permanently discontinued from the study and/or from the study treatment in the following circumstances:

- Enrollment in any other clinical trial involving an investigational product or enrollment in any other type of medical research judged not to be scientifically or medically compatible with this study.
- Investigator/Physician Decision
 - The investigator/physician decides that the patient should be discontinued from the study or study drug(s).
 - The patient, for any reason, requires treatment with another therapeutic agent that has been demonstrated to be effective for treatment of the study indication; discontinuation from the study drug(s) occurs prior to introduction of the other agent.
- Patient Decision
 - The patient or the patient's designee (for example, parents or legal guardian) requests to be discontinued from the study or study drug. No follow-up procedures will be performed for patients who withdraw informed consent, unless he or she has explicitly provided permission and consent.
- Sponsor Decision
 - Lilly, in consultation with the collaborator, stops the study or stops the patient's participation in the study for medical, safety, regulatory, or other reasons consistent with applicable laws, regulations, and GCP.
- The patient experiences a Grade ≥ 3 infusion reaction.
- The patient has radiographic evidence of progressive disease or significant symptomatic disease deterioration characterized as progression of disease, in the opinion of investigator, in the absence of radiographic evidence of progressive disease.

Exceptions for continuing study treatment beyond confirmed radiographic progression may be made on a case-by-case basis for patients who are believed to be clinically benefiting from study treatment, and the investigator and the sponsor agree that continuing study treatment is in the patient's best interest.

- The patient experiences unacceptable toxicity (for example, an AE that, in the opinion of the investigator or the sponsor, contraindicates further dosing).
- The patient is noncompliant with study procedures and/or treatment (Section 7.6).
- The patient becomes pregnant or intends to become pregnant during the study.
- The patient begins treatment with alternative anticancer therapy, including another investigational agent.
- The administration of study drug is delayed for more than 28 days.
 - For the patients treated with the LY3022855-plus-tremelimumab combination, a delay of up to 28 days between doses is allowed for Cycles 1 through 6, and up to 60 days between doses for Cycles 7 and beyond.

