5.1.3. Summary of the Rationale for Amendment (c)

Amendment (c) was created to incorporate the following changes:

- Dose modification and toxicity management guidelines for durvalumab was updated per new guidance from AstraZeneca.
- Added clarification about testing for mutations in *EGFR* or *ALK* genes for patients in Part B (NSCLC cohort only).
- Updated information about tumor biopsy samples to make it consistent across sections.
- Updated treatment delay criteria to provide consistency across the protocol.

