7.2.1.1. LY3022855

Eligible patients will receive LY3022855 as an I.V. infusion administered over a minimum duration of 30 minutes and a maximum duration of 4 hours, based on the known safety and stability of the prepared drug. The infusion rate should not exceed 25 mg/minute. Suggested infusion times are as follows:

- 90 minutes for the first infusion; if no infusion-related reaction (IRR) is observed, decrease the infusion time to 60 minutes for the second infusion
- 60 minutes for the second infusion; if no IRR is observed, decrease the infusion time to 30 minutes for the third infusion
- 30 minutes for the third and subsequent infusions

If, at any time, a patient experiences an IRR, the infusion time should not be decreased.

Premedication is not recommended to be administered prior to the first infusion of LY3022855. However, if the patient experiences a Grade 1 or 2 IRR, premedication must be provided prior to any subsequent doses of LY3022855. The choice of premedication is to be made after discussion and agreement between the investigator and sponsor. In such cases (Grade 1 or 2 IRRs), administration of steroids should be avoided, if possible. If an IRR Grade ≤ 2 occurs during or after LY3022855 administration and the patient's condition allows it, treatment with durvalumab or tremelimumab will proceed as planned. Patients experiencing an IRR Grade ≥ 3 will be permanently discontinued from study treatment.

LY3022855 may be administered up to 3 days AFTER the scheduled dosing date and up to 4 days BEFORE the next scheduled dosing date to accommodate for patient vacations, holidays, inclement weather or other unforeseen circumstances. If, at any time, a dose is to be administered beyond the 3-day window, that dose is to be skipped. A maximum of 28 days between administered doses is allowed for delays due to adverse events.

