7.2.4.1. Dose Delays for Adverse Events

Study treatment may be held for a maximum of 28 days; see exception for an immune-related AE below. If appropriate, and in the opinion of the investigator and upon agreement with the sponsor, study treatment may resume upon resolution of clinically significant AEs to baseline or improvement to Grade <2. If AEs, see exception for an immune-related AE, do not resolve to baseline or improve to Grade <2 within 28 days following the last administered dose, study treatment should be permanently discontinued and the patient should be discontinued from the trial. If treatment is held, the day of treatment should continue as if no drug interruption has occurred. For example, if study drug is held on D6 of a cycle and AEs have resolved by D10 (4 days later), the study drugs should be resumed per the original schedule. If the original schedule results in a study drug being held for >28 days, the study drug may not be resumed. One or both study drugs may be held, resumed, or discontinued.

If the AE is an immune related AE as outlined in [Attachment 7](#), and if the treatment management guidelines outlined in [Attachment 7](#) are followed and documented in the patient's medical record, treatment may be held for >28 days to allow taper of high dose steroids. Treatment may resume in this setting only upon resolution of immune AEs to baseline or improvement to Grade <2, and only if deemed clinically appropriate by the treating physician and agreed to by the sponsor. If steroids cannot be tapered as outlined in [Attachment 7](#), and/or AEs do not resolve to < Grade 2, the patient may not be resumed on study treatment.

For the purposes of documentation, the investigator must assess if the toxicity is considered at least possibly related to study treatment (that is, the combination regimen) and if the AE is considered to be immune related. Investigators are encouraged to consult the sponsor for additional guidance.

For AEs that are considered at least possibly related to study treatment, the following dose adjustment guidance may be applied:

- Treat each of the toxicities with maximum supportive care (including holding the study drug[s] suspected of causing the toxicity where required).
- If the symptoms promptly resolve with supportive care, consideration should be given to continuing the same dose of study drugs along with appropriate continuing supportive care.

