	
Grade 1 (Diarrhea: stool frequency of <4 over baseline per day) (Colitis: asymptomatic; clinical or diagnostic observations only)
	No dose modifications.	
For Grade 1:
 
 Monitor closely for worsening symptoms. Consider symptomatic treatment, including hydration, electrolyte replacement, dietary changes (eg, American Dietetic Association colitis diet), and loperamide. Use probiotics as per treating physician's clinical judgment.
	
Grade 2 (Diarrhea: stool frequency of 4 to 6 over baseline per day) (Colitis: abdominal pain; mucus or blood in stool)
	
Hold study drug/study regimen until resolution to Grade ≤ 1
 
 If toxicity worsens, then treat as Grade 3 or Grade 4. If toxicity improves to Grade ≤ 1, then study drug/study regimen can be resumed after completion of steroid taper. 	
For Grade 2:
 
 Consider symptomatic treatment, including hydration, electrolyte replacement, dietary changes (eg, American Dietetic Association colitis diet), and loperamide and/or budesonide. Promptly start prednisone 1 to 2 mg/kg/day PO or IV equivalent. If event is not responsive within 3 to 5 days or worsens despite prednisone at 1 to 2 mg/kg/day PO or IV equivalent, GI consult should be obtained for consideration of further workup, such as imaging and/or colonoscopy, to confirm colitis and rule out perforation, and prompt treatment with IV methylprednisolone 2 to 4 mg/kg/day started. If still no improvement within 3 to 5 days despite 2 to 4 mg/kg IV methylprednisolone, promptly start immunosuppressives such as infliximab at 5 mg/kg once every 2 weeks^a. Caution: it is important to rule out bowel perforation and refer to infliximab label for general guidance before using infliximab. Consider, as necessary, discussing with study physician if no resolution to Grade ≤ 1 in 3 to 4 days. Once the patient is improving, gradually taper steroids over ≥ 28 days and consider prophylactic antibiotics, antifungals, and anti-PJP treatment (refer to current NCCN guidelines for treatment of cancer-related infections [Category 2B recommendation]).^a

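### For immune-related holds over 28 days, Protocol 6.3.2 and 7.2.1.1 end treatment while 7.2.4.1 and Attachment 7 allow it to resume, and the way of counting the days is not defined

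*Protocol*

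**What the plan says.** - **Protocol 6.3.2 (discontinuation).** The list opens: "Patients will be permanently discontinued from the study and/or from the study treatment in the following circumstances". One entry reads: "The administration of study drug is delayed for more than 28 days". A sub-entry for the tremelimumab combination keeps 28 days for Cycles 1 to 6 and allows "up to 60 days between doses for Cycles 7 and beyond". Immune-related events are not mentioned and 7.2.4.1 is not cited.
- **Protocol 7.2.1.1 (LY3022855).** "A maximum of 28 days between administered doses is allowed for delays due to adverse events". No exception is given.
- **Protocol 7.2.1.2 (durvalumab).** A 28-day maximum, with a pointer to 7.2.4.1 for immune-related events.
- **Protocol 7.2.1.3 (tremelimumab).** 28 days in Cycles 1 to 6 and 60 days afterwards, with no pointer.
- **Protocol 7.2.4.1 (dose delays).** "Study treatment may be held for a maximum of 28 days; see exception for an immune-related AE below". For an immune-related event managed and documented under Attachment 7, "treatment may be held for >28 days to allow taper of high dose steroids". Resumption then requires resolution to baseline or below Grade 2, the treating physician's judgment and the sponsor's agreement.
- **Attachment 7.** For Grade 2 diarrhea/colitis, once the event has improved, "then study drug/study regimen can be resumed after completion of steroid taper"; the same row sets the taper at 28 days or more. Grade 2 pneumonitis, hepatitis and nephritis, and Grade 3 diarrhea/colitis, also combine a taper of at least 28 days with resumption only after it is complete.
- **Protocol 5.1.3.** A stated purpose of Amendment (c): "Updated treatment delay criteria to provide consistency across the protocol".

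**The concern.** For an immune-related hold that passes 28 days, one section ends treatment for good and another lets it resume. Within a single regimen the drugs also appear to differ: read literally, durvalumab may restart after a long hold while LY3022855, the drug under study, may not.

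Safety and tolerability are a primary objective (Protocol 5.2.1). SAP 6.4 summarizes reasons for discontinuing treatment and study. SAP 6.8.1 summarizes cycles received, duration on therapy, cumulative dose, dose intensity and relative dose intensity. All of these depend on which section was followed, and the cohorts are small. The choice also decides whether a patient permanently loses treatment.

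**Working it through.** The plan gives no figure to reproduce. The check sets the rules side by side and then counts days.

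**Step 1. The same patient under each section.** Take an immune-related event managed under Attachment 7, with a hold longer than 28 days and the patient outside the tremelimumab Cycle 7+ allowance.

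| Section | Consequence |
|---|---|
| 6.3.2 | Permanent discontinuation |
| 7.2.1.1 (LY3022855) | Further dosing not allowed |
| 7.2.1.2 (durvalumab) | Defers to 7.2.4.1 |
| 7.2.1.3 (tremelimumab, Cycles 1–6) | Beyond the allowed delay |
| 7.2.4.1 | May resume if the conditions are met |

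**Step 2. Does a 28-day taper produce such a hold?** That depends on the clock, and the Protocol uses several: *delayed* in 6.3.2, *between administered doses* in 7.2.1.1 to 7.2.1.3, and both *held* and *following the last administered dose* in 7.2.4.1.

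Inputs: a taper of exactly 28 days (the Attachment 7 minimum); event onset on day o after the last dose, for each o from 1 to the dosing interval I; s days from onset to the start of the taper, assumed to be 0, 3, 5 or 10; dosing resumed on the original schedule (7.2.4.1).

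- End of taper: E = o + s + 28
- Day of the resumed dose, counted from the last dose: R = I × ceil(E / I)
- Delay past the first missed dose: D = R − I

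*Clock from the last dose.* The smallest E is 1 + 0 + 28 = 29, so every full taper passes 28 days.

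*Clock from the first missed dose.* Example for weekly dosing with s = 3. Onset on day 4 gives E = 35, R = 35, D = 28, which is not over the limit. Onset on day 5 gives E = 36, R = 42, D = 35, which is over. For all onset days:

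| Schedule | Range of D | Onset days with D > 28, for s = 0 / 3 / 5 / 10 | Shortest R |
|---|---|---|---|
| Weekly (LY3022855) | 28–42 | 0/7, 3/7, 5/7, 7/7 | 35 |
| Every 2 weeks (durvalumab) | 28–42 | 0/14, 3/14, 5/14, 10/14 | 42 |
| Every 4 weeks (tremelimumab) | 28–56 | 0/28, 3/28, 5/28, 10/28 | 56 |

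*Clock from dose to dose.* R is at least 35 days on every schedule in the table, so the limit is always passed. This reading cannot be meant for tremelimumab: a 28-day limit equals the planned 4-week interval, and 60 days is shorter than the planned 84-day interval.

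For tremelimumab every 12 weeks, D ranges from 0 to 84 days. It exceeds the 60-day allowance on 28/84, 31/84, 33/84 and 38/84 onset days for the same values of s.

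**Step 3. Other limits.** Several Attachment 7 rows (Grade 3 rash and neurotoxicity; Grade 2 and 3 peripheral neuromotor syndromes and myositis) discontinue for non-resolution only after 30 days, which is also longer than 28.

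**Step 4. Weight of one patient.** One patient counted differently moves a discontinuation percentage by 1/20 = 5 points in a Part B cohort, and by 1/6 ≈ 17 to 1/3 ≈ 33 points in a Part A cohort of 6 or 3.

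**The case against.** The best defense is that 7.2.4.1 is the specific rule and 6.3.2 the general one. Section 7.2.4.1 restates the 28-day limit, announces an exception and attaches conditions. It speaks of study treatment as a whole and says that one or both drugs may be resumed, so it is not confined to durvalumab. This is a reasonable reading, but it does not settle the matter. Section 6.3.2 writes out exceptions where it intends them (treatment beyond progression; tremelimumab from Cycle 7) and gives none here. Section 7.2.1.1 is itself specific to delays caused by adverse events.

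Three further points stand and limit the finding:

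- Resumption after a long hold needs the sponsor's agreement, which restrains differences between sites. A reader might infer that sites will diverge freely; the documents do not support that. What remains is that a site applying 6.3.2 or 7.2.1.1 as written may never ask.
- DLTs are Cycle 1 events (7.2.2.1) and escalation rests on their count (7.2.2.2), so a hold over 28 days does not change those counts.
- All analyses are descriptive (SAP 6.1). The effect is on the disposition and exposure summaries, and the documents give no expected frequency of such holds.

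**Conclusion.** The inconsistency is real and confined to immune-related holds that exceed 28 days, outside the tremelimumab Cycle 7+ allowance. For these, 6.3.2 mandates discontinuation and 7.2.1.1 bars LY3022855, while 7.2.4.1 conditionally permits resumption.

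Stronger readings are tempting but not supported:

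- *Any delay over 28 days ends treatment under 6.3.2.* It does not; the entry beneath that rule allows 60 days for tremelimumab from Cycle 7.
- *Section 7.2.4.1 makes patients resume.* It permits resumption under conditions, and keeps the 28-day limit for other adverse events.
- *Every event treated with a taper breaches 6.3.2.* Attachment 7 itself permanently discontinues several of them, including Grade 3–4 pneumonitis, nephritis and myocarditis and Grade 4 colitis, so there is no conflict there. For the others, a breach is certain when counting from the last dose. Counting from the first missed dose, it ranges from no onset days (taper starting at onset) to all of them (weekly dosing, taper starting 10 days later).

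These counts rest on a taper of exactly 28 days, the assumed values of s and resumption on the original schedule. A longer taper can only lengthen the delay. The point should be corrected, but it does not undermine dose escalation. No position is taken on which clinical limit is right.

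**What to change.** 1. Reconcile Protocol 6.3.2, 7.2.1.1 and 7.2.1.3 with 7.2.4.1 and Attachment 7, so that an immune-related hold over 28 days has one stated consequence.
2. State for LY3022855, durvalumab and tremelimumab separately whether the immune-related exception applies, and how it relates to the tremelimumab 60-day allowance.
3. Define once how the days are counted (from the last administered dose, from the first missed scheduled dose, or from dose to dose) and use that term in every section, including 7.2.1.2.

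The clinical team should choose the content of the rule. The statistical need is that the discontinuation and exposure summaries rest on a single rule. The cost is protocol wording only, with no new procedures, data or sample size.

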6.3.3. Patients Lost to Follow-Up

A patient would be considered lost to follow-up if he or she repeatedly fails to return for scheduled visits and is unable to be contacted by the study site.

6.3.4. Discontinuation of Study Sites

Study site participation may be discontinued if Lilly, the investigator, or the ethical review board (ERB) of the study site judges discontinuation of study site participation necessary for any scientific, medical, safety, regulatory, ethical, or other reasons consistent with applicable laws, regulations, and GCP.

6.3.5. Discontinuation of the Study

The study will be discontinued if Lilly, while considering the rights, safety, and well-being of the patient(s), judges discontinuation of the study necessary for any scientific, medical, safety, regulatory, ethical, or other reasons consistent with applicable laws, regulations, and GCP.

7. Treatment

7.1. Materials and Supplies

Clinical study materials will be labeled according to the country's regulatory requirements.

7.1.1. LY3022855

LY3022855 Injection for infusion is supplied at 5 mg/mL strength as a solution dosage, in glass vials with an elastomeric closure. Each vial of LY3022855 Injection for infusion contains 20 mL of the drug product (100 mg/20-mL vial). Vials of LY3022855 Injection for infusion should be stored refrigerated at 2°C to 8°C. The drug product is formulated to contain the active LY3022855 in 10mM histidine, 100mM glycine, 100mM arginine, and 0.01% polysorbate 80 at pH 6.0. LY3022855 is a clear or slightly opalescent and colorless or slightly yellow liquid without visible particles. LY3022855 will be administered as an I.V. infusion. The dose is prepared and infused at room temperature. LY3022855 will be diluted in normal saline to a final volume of 250 mL. Lilly instructions regarding dilution requirements should be followed.

